Sponsor	ANA Therapeutics, Inc. [name]
Principal Investigator	[name] WCCT Global [name]
Medical Monitor	[name] [name]
Biostatistics and Pharmacokinetics	[name] Inference, Inc. [name]
Clinical laboratory	Innovative Bioanalysis, LLC [name]
Bioanalytical laboratory (PK-analysis)	Medpace Bioanalytical Laboratories [name] [contact] [contact]

Protocol Amendment History

Date	Description
24-Dec-20	
Amendment 1
 
The protocol is amended to address comments received by the FDA as follows:
 
- Revising the Inclusion criteria pulse rate limits from 40 -100 bpm to 50 – 100 bpm- Providing reference laboratory values that will be used to determine if laboratory results are considered clinically significant- Providing a standard toxicity grading scale- Providing of detailed individual and dose level stopping criteria based upon the known safety profile and mechanism of action of ANA001 (niclosamide)- Limiting the total daily dose in the MAD portion of the protocol to 2000 mg
	
Page 8. MAD
 
Total daily doses are anticipated to range between will not exceed 2000 mg and 4500 mg of ANA001.

	
Page 18. Section 3.3 Benefit/Risk Assessment
 
The current SAD/MAD study is designed to explore the safety and PK of dosing greater than up to 2000-3000 mg/day as a single dose and regimens not to exceed 2000 mg/day as divided doses BID or TID.

	
Page 20. MAD
 
Total daily doses are anticipated to range between will not exceed 2000 mg and 4500 mg of ANA001.

	
Page 21. Section 5.5 Justification for Dose
 
The current study is designed to assess the safety of single doses of ANA001 exceeding up to 3000 2,000 mg and multiple dosing regimens up to not to exceed 2000 mg daily divided either BID or TID.

Date	Description
24-Dec-20	
Amendment 1
 
Page 22. Section 6.1 Inclusion Criteria 6. Pulse rate between 40 50 and 100 beats per minute (bpm)
 
Page 23. Section 6.2 Exclusion Criteria Clinically significant abnormal values for hematology, clinical chemistry, or urinalysis at screening as deemed appropriate by the Investigator assessed per Appendix 6.
 
Page 25. 7.2 Dose Modification Following review of the safety and PK data of three SAD cohorts, a fourth cohort may be added, not to exceed 4500 mg. Total daily doses are anticipated to be between will not exceed 2000 mg and 4500 mg.
 
Page 31. Section 9.1.4 Clinical Safety Laboratory Assessments The Investigator must review the laboratory report, document this review, and record any clinically relevant changes (as per the reference laboratory values [Appendix 6]) occurring during the study in the AE section of the CRF. All laboratory tests with values considered clinically significantly abnormal during participation in the study should be repeated until the values return to normal or baseline or are no longer considered clinically significant by the Investigator or medical monitor as per the reference laboratory values in Appendix 6.
 
If laboratory values from non-protocol specified laboratory assessments performed at the institution's local laboratory require a change in participant management or are considered clinically significant by the Investigator as given in Appendix 6 (e.g., SAE or AE or dose modification), then the results must be recorded in the CRF.
 
Page 33. Insertion of 9.3 Stopping Rules in Response to SAE

Date	Description
24-Dec-20	
Amendment 1
 
Dose-limiting toxicity AEs will be defined as Grade ≥ 3, treatment-emergent, treatment-related laboratory abnormalities (Appendix 6) or AEs per the grading system by US Department of Health and Human Services (CTCAE, Version 5.0).
 
The following Stopping Criteria will be used:
 
Clinical Findings:
 
1. Anaphylaxis or Grade ≥ 3 skin rash or pruritis2. Grade ≥ 3 nausea, emesis or diarrhea 
Laboratory Findings:
 
1. Evidence of new onset of acute renal or hepatic failure, defined by increases in BUN, creatinine, or LFTs (AST, ALT, Alkaline phosphatase) that reflect new evidence of Grade 3 thresholds for liver function tests, for creatinine, and for electrolytes attributable to the administration of drug in the context of the Investigator's evaluation.2. Evidence of acute infection or inflammation, defined by changes in the WBC and differential indices, attributable to the administration of drug in the context of the Investigator's evaluation.3. Any "unexpected" Grade ≥ 3 Laboratory test result. 
If one of the above clinical or laboratory criteria for stopping occurs in any subject, further study recruitment and subject dosing will be halted until a full safety assessment can be completed. Unblinding of the affected subject will be performed and the PI and Sponsor will review the totality of clinical data and any other circumstances possibly related to the "Stopping Criteria" findings to determine if the study can be resumed, modified, or will be permanently terminated.
 
Page 33. Section 9.3 Treatment of Overdose

Date	Description
24-Dec-20	
Amendment 1
 
For this study, any dose of ANA001 greater than 4500 3000 mg within a 24-hour time period will be considered an overdose.

	
Page 37. Section 11 References Inserted reference in relation to Stopping rules: US Department of Health and Human Services. Common Terminology Criteria for Adverse Events (CTCAE). Version 5.0. Published: November 27, 2017.
 
Page 50. Appendix 4 Any abnormal laboratory test results (hematology, clinical chemistry, or urinalysis) or other safety assessments (e.g., ECG, radiological scans, vital signs measurements), including those that worsen from baseline, considered clinically significant in the medical and scientific judgment of by the Investigator per Appendix 6 (i.e., not related to progression of underlying disease).
 
Insertion of Appendix 6 Potentially Clinically Significant Laboratory Criteria

	
Editorial Changes
 
Language in bold has been added to the document for clarification purposes. Minor formatting and typographical errors were corrected throughout the protocol.
 
Page 7. Section 1 Synopsis and Page 15. Section 3.1 Study Rationale
 
ANA001 is a new formulation containing 250 mg niclosamide per capsule. Although other formulations containing niclosamide (ANA001) have been studied for tapeworm infections and other potential human uses, limited systemic PK/PD data exists in the literature. To ensure proper systemic levels of niclosamide are achieved for therapeutic effect, a SAD/MAD study with ANA001 capsules is necessary.
 
Page 7. Section 1 Synopsis
 
ANA001 capsule containing 250 mg niclosamide, administered orally as 4, 6, 8 or 12 capsules with a light meal (500 to 750 cal) or snack.

Date	Description
24-Dec-20	
Amendment 1
 
All participants on active treatment who contributed at least one post dose blood sample, evaluable for drug PK concentration will be included in the PK analysis.
 
Global change throughout protocol
 
Replaced 'postdose' with 'after dosing' and 'predose' with 'before dosing' except with analysis timepoints.
 
Page 14. Section 3 Introduction
 
Due to its pleiotropic pharmacologic activity, niclosamide has been and is being continues to be studied in for a variety of other clinical indications.
 
COVID-19 is results in a cytokine release syndrome.
 
Page 43. Appendix 1
 
Updated as per changes in text.

Table of Contents

Protocol Amendment History	5
1. Synopsis.....	13
2. Schedule of Activities (SoA)	16
3. Introduction.....	20
3.1. Study Rationale.....	21
3.2. Background.....	21
3.2.1. Chemical Name/Structure	22

Appendix 5: Contraceptive Guidance and Collection of Pregnancy Information	64	

[Appendix 6: Potentially Clinically Significant Laboratory Criteria68](#)

List of Tables

Table 1	Schedule of Activities for SAD.....	16
Table 2	Schedule of Activities for MAD	17
Table 3	Schedule of PK Sampling for MAD	19
Table 4	Protocol-Required Safety Laboratory Assessments	53
Table 5:	Highly Effective Contraceptive Methods.....	65

List of Figures

Figure 1	Phylogenetic Tree Showing Antiviral Effects of Niclosamide Against Various Virus Families	21
----------	---	----

1. Synopsis

Protocol Title: A Randomized, Double-Blind, Single and Multiple Ascending Dose Study to Assess the Safety and Pharmacokinetics of ANA001 in Healthy Adults

Short Title: A single ascending dose (SAD) and multiple ascending dose (MAD) PK study of ANA001 in healthy adults

Rationale:

ANA001 is a new formulation containing 250 mg niclosamide per capsule. Although other formulations containing niclosamide (ANA001) have been studied for tapeworm infections and other potential human uses, limited systemic PK/PD data exists in the literature. To ensure proper systemic levels of niclosamide are achieved for therapeutic effect, a SAD/MAD study with ANA001 capsules is necessary.

Objectives and Endpoints

Objectives	Endpoints
Primary	

To assess safety and tolerability of single oral daily doses of ANA001 (1000 mg, 2000 mg and 3000 mg)To assess safety and tolerability of multiple daily oral doses (twice daily [BID] or thrice daily [TID]) of ANA001 for 7 days	
Incidence of adverse events (AEs), serious AEs (SAEs), study drug discontinuation due to an AE (MAD portion only), use of concomitant medications, and change from baseline in clinical laboratory tests, vital signs, electrocardiograms (ECG), and physical examinations
Secondary	

To assess the PK of single and multiple doses of ANA001	
AUC_{0-t}, AUC_{0-last}, $AUC_{0-\infty}$ (SAD only), C_{max}, t_{max}, $t_{1/2}$, CL/F, V_z/F

Overall Design:

This is a randomized, double-blind study to be conducted in two parts: single ascending dose (SAD) and multiple ascending dose (MAD). Potential participants for each part will undergo screening procedures within 30 days of enrolment.

SAD

On Day -1, eligible participants will be randomly assigned to active drug or placebo in an 8:2 ratio. On Day 1, following an overnight fast of at least 10 hours, participants will receive their assigned treatment (1000 mg, 2000 mg, or 3000 mg of ANA001) with a standardized light meal (500 to 750 cal). A baseline ECG will be performed at Screening and at 3 hours after dosing. Blood pressure and heart rate will be measured every 8 hours while confined to the clinic. Blood for PK will be collected before dosing and at 0.5, 1, 2, 4, 6, 8, 10, 12 and 24 hours after dosing. Participants will be discharged on Day 2 following the 24-hour PK sample and completion of clinical laboratory tests and physical examination. They will return on Day 7 (± 2) for follow-up procedures including physical examination, laboratory tests, and assessment of AEs and concomitant medication use.

MAD

On Day -1, eligible participants will be randomly assigned to active drug or placebo in a 10:2 ratio on a BID (q12h) or TID (q8h) schedule, to be determined based on the PK results of the SAD cohorts. Total daily doses will not exceed 2000 mg of ANA001. On Days 1 through 7, participants will receive their assigned treatment in the morning with a standardized light meal (500 to 750 cal) following an overnight fast of at least 10 hours. Afternoon or evening doses will be given with a light snack. A baseline ECG will be performed at Screening and at 3 hours after the second dose on Day 7. Blood pressure and heart rate will be measured every 8 hours while confined to the clinic.

During BID dosing, blood for PK will be collected on Days 1 and 7 before dosing and at 0.5, 1, 2, 4, 6, 8, 10, and 12 hours after dosing. Blood samples will also be collected on Days 2, 4, 6, and 8 before dosing and before the 12 hour dose on Days 2, 4, and 6.

During TID dosing, blood for PK will be collected on Days 1 and 7 before dosing and at 0.5, 1, 2, 4, 6, and 8 hours after dosing. Blood samples will also be collected on Days 2, 4, 6, and 8 before dosing, and before the 8 hour dose on Days 2, 4, and 6, and before the 16 hour dose on Day 6.

Participants will be discharged on Day 8 following the last PK sample and completion of clinical laboratory tests and physical examination. They will return on Day 15 (± 2) for follow-up procedures including physical examination, laboratory tests, and assessment of AEs and concomitant medication use.

Number of Participants:

A minimum of 30 participants will be enrolled in the SAD part and up to 36 participants in the MAD part. At least 3 participants of each sex will be included in each cohort.

Treatment Groups and Duration:

SAD

Cohort S1: 1000 mg (n=8) or placebo (n=2), single dose

Cohort S2: 2000 mg (n=8) or placebo (n=2), single dose

Cohort S3: 3000 mg (n=8) or placebo (n=2), single dose

MAD

Cohort M1: xx mg (n=9) or placebo (n=3) BID or TID for 7 days

Cohort M2: xx mg (n=9) or placebo (n=3) BID or TID for 7 days

Cohort M3: xx mg (n=9) or placebo (n=3) BID or TID for 7 days

Investigational Product, Dose, and Mode of Administration

ANA001 capsule containing 250 mg niclosamide, administered orally as 4, 6, 8 or 12 capsules with a light meal (500 to 750 cal) or snack.

Statistical Methods

Sample Size Determination:

Sample size was not based on statistical considerations.

Safety Analysis:

All participants who received at least one dose of study drug will be included in the safety analysis. Safety will be assessed by the incidence and frequency of AEs, and changes in physical examinations, vital signs, clinical laboratory tests, and ECGs. Results will be summarized using descriptive statistics (mean, standard deviation [SD], coefficient of variation [%CV], median, minimum, maximum).

Pharmacokinetic Analysis:

All participants on active treatment who contributed at least one post dose blood sample, evaluable for drug PK concentration will be included in the PK analysis. PK parameters, calculated using non-compartmental models, include $AUC_{0-\infty}$, AUC_{0-t} , $AUC_{0\text{-last}}$, C_{max} , t_{max} , $t_{1/2}$, CL/F , and V_z/F . Results will be summarized using descriptive statistics (mean, standard deviation [SD], coefficient of variation [%CV], median, minimum, maximum). Plasma concentration-time profiles will be plotted.

2. Schedule of Activities (SoA)

Table 1 Schedule of Activities for SAD

	Screening	In-Patient		Discharge	Follow-up
Study Day	-30 to -2	-1	1	2	7±2
Study Procedures					
COVID Pre-screen informed consent	X				
Full study informed consent	X				
Medical history	X				
Prior medications	X				
Physical examination	X				
Abbreviated PE		X	X	X	X
Viral Serology (HIV, HCV, HBV)	X				
Urine alcohol and drug screen	X	X			
Inclusion / exclusion criteria	X	X			
Pregnancy test for WOCBP	X	X			
Randomization		X			
CPU Admission & Confinement		X	X		
CPU Discharge				X	
Drug Administration ^a				X	
Vital signs ^b	X	X	X	X	X
Height	X				
Weight	X	X			
ECG ^c	X		X		
Hematology	X	X		X	X

	Screening	In-Patient		Discharge	Follow-up	
Study Day	-30 to -2	-1	1	2	7±2	
Study Procedures						
Serum chemistry	X	X		X	X	
Urinalysis	X			X	X	
Pharmacokinetics ^d			X	X		
Adverse events			Continuous			
Concomitant medications			Continuous			

WOCBP = woman of child-bearing potential

- a.) Administered with Standardized light meal
- b.) Blood pressure and heart rate supine for 3 to 5 mins and every 8 hours during CPU confinement
- c.) Supine for 5 mins at Screening and 3 hours after dosing
- d.) 4 mL before dosing and 0.5, 1, 2, 4, 6, 8, 10, 12 and 24 hr after dosing

Table 2 Schedule of Activities for MAD

	Screening	Confinement/Treatment Period									Discharge	Follow-up	
Study Day	-30 to -2	-1	1	2	3	4	5	6	7	8		D15±2	
Study Procedures													
COVID Pre-screen ICF	X												
Full study informed consent	X												
Medical history	X												
Prior medications	X												
Physical examination	X												
Abbreviated PE		X		X			X			X		X	
Viral Serology (HIV, HCV, HBV)	X												

	Screening	Confinement/Treatment Period							Discharge	Follow-up	
Study Day	-30 to -2	-1	1	2	3	4	5	6	7	8	D15±2
Study Procedures											
COVID Surveillance (ELISA)		+ Swab			X			X			
Urine alcohol and drug screen	X	X									
Pregnancy test for WOCBP	X	X									
Inclusion / exclusion criteria	X	X									
Randomization		X									
CPU Admission & Confinement		X	X	X	X	X	X	X	X		
CPU Discharge										X	
Drug Administration ^a			X	X	X	X	X	X	X		
Vital signs ^b	X	X	X	X	X	X	X	X	X		X
Height	X										
Weight	X										
ECG ^c	X								X		
Hematology	X	X		X			X			X	X
Serum chemistry	X	X		X			X			X	X
Urinalysis	X			X			X			X	X
Pharmacokinetics ^d			X	X	X	X	X	X	X		
Adverse events		Continuous									
Concomitant medications		Continuous									

WOCBP = woman of child-bearing potential

- a.) Administered with standardized light meal (500 to 750 cal) in AM and light snack (PM) if BID (q12h) or TID (q8h) daily on days 1 through 6 and a single AM dose on day 7
- b.) Blood pressure and heart rate supine for 3 to 5 mins and every 8 hours during confinement
- c.) Supine for 5 mins at Screening and at 3 hours after second dose on Day 7
- d.) see Table 3

Table 3 Schedule of PK Sampling for MAD

	PK Sampling (4 mL) Study Day BID Dosing							
Time (hr)	1	2	3	4	5	6	7	8
Pre-dose	X ^a	X ^a		X ^a		X ^a	X ^a	X ^a
0.5	X						X	
1	X						X	
2	X						X	
4	X						X	
6	X						X	
8	X						X	
10	X						X	
12	X	X ^a		X ^a		X ^a	X ^a	
	PK Sampling (4 mL) Study Day TID Dosing							
Time (hr)	1	2	3	4	5	6	7	8
Pre-dose	X ^a	X ^a		X ^a		X ^a	X ^a	X ^a
0.5	X						X	
1	X						X	
2	X						X	
4	X						X	
6	X						X	
8	X	X ^a		X ^a		X ^a	X ^a	

^a Pre-dose

3. Introduction

Niclosamide is a chlorinated salicylanilide with anthelmintic, antiviral and anti-inflammatory activity being developed as a potential treatment for COVID-19. Niclosamide was discovered in 1958, and was approved by the Food and Drug Administration (FDA) in 1982 under New Drug Application (NDA) 018669 (Bayer Pharmaceuticals) for the treatment of tapeworm infections, although it has since been voluntarily discontinued from marketing in the United States by Bayer. Niclosamide is approved in several other countries for the treatment of tapeworm infections and is on the World Health Organization's List of Essential Medicines. Due to its pleiotropic pharmacologic activity, niclosamide has been and continues to be studied for a variety of other clinical indications.

ANA Therapeutics is developing ANA001, an orally administered niclosamide formulation containing 250 mg niclosamide per capsule, to treat adult patients with coronavirus disease of 2019 (COVID-19). COVID-19 results in a cytokine release syndrome ([Hirano and Murakami, 2020](#)) that is associated – amongst others - with acute respiratory distress syndrome (ARDS), a widespread inflammation in the lungs, and increased blood clotting. Niclosamide is a promising oral therapeutic which has both antiviral and anti-inflammatory properties and a long history of safety in humans.

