5.1. Overall Design

This is a randomized, double-blind study to be conducted in two parts: single ascending dose (SAD) and multiple ascending dose (MAD). Potential participants for each part will undergo screening procedures within 30 days of enrolment.

SAD

On Day -1, eligible participants will be randomly assigned to active drug or placebo in an 8:2 ratio. On Day 1, following an overnight fast of at least 10 hours, participants will receive their assigned treatment (1000 mg, 2000 mg, or 3000 mg of ANA001) with a standardized light meal (500 to 750 cal). A baseline ECG will be performed at Screening and at 3 hours after dosing. Blood pressure and heart rate will be measured every 8 hours while confined to the clinic. Blood for PK will be collected before dosing and at 0.5, 1, 2, 4, 6, 8, 10, 12 and 24 hours after dosing. Participants will be discharged on Day 2 following the 24-hour PK sample and completion of clinical laboratory tests and physical examination. They will return on Day 7 (± 2) for follow-up procedures including physical examination, laboratory tests, and assessment of AEs and concomitant medication use.

MAD

On Day -1, eligible participants will be randomly assigned to active drug or placebo in a 9:3 ratio on a BID (q12h) or TID (q8h) schedule, to be determined based on the PK results of the SAD cohorts. Total daily doses will not exceed 2000 mg of ANA001. On Days 1 through 7, participants will receive their assigned treatment in the morning with a standardized light meal (500 to 750 cal) following an overnight fast of at least 10 hours. Afternoon or evening doses will be given with a light snack. A baseline ECG will be performed at Screening and at 3 hours after the second dose on Day 7. Blood pressure and heart rate will be measured every 8 hours while confined to the clinic.

During BID dosing, blood for PK will be collected on Days 1 and 7 before dosing and at 0.5, 1, 2, 4, 6, 8, 10, and 12 hours after dosing. Blood samples will also be collected on Days 2, 4, 6, and 8 before dosing and before the 12 hour dose on Days 2, 4, and 6.

During TID dosing, blood for PK will be collected on Days 1 and 7 before dosing and at 0.5, 1, 2, 4, 6, and 8 hours after dosing. Blood samples will also be collected on Days 2, 4, 6, and 8 before dosing, before the 8 hour dose on Days 2, 4, and 6, and before the 16 hour dose on Day 6.

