9.1.3. Electrocardiograms

A single ECG will be obtained for screening and at 3 hours after dosing during the SAD portion of the study and at Screening and 3 hours after dosing on Day 7 during the MAD portion. An ECG machine that automatically calculates the heart rate and measures PR, QRS, QT, and QTc intervals will be used.

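### The MAD schedule gives one morning dose on Day 7, yet times its only post-baseline ECG from a second Day 7 dose

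*Protocol*

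**What the plan says.** **Day 7 dosing.** Protocol Table 2, footnote a, has BID or TID dosing "daily on days 1 through 6 and a single AM dose on day 7". SAP 3.2 repeats the footnote. The narrative sections (Protocol 1 and 5.1, SAP 3) say "On Days 1 through 7, participants will receive their assigned treatment in the morning", then "Afternoon or evening doses will be given with a light snack", and make no exception for Day 7. The cohort lists read, for example, "Cohort M1: xx mg (n=9) or placebo (n=3) BID or TID for 7 days".

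**ECG timing.** Footnote c of the same table reads "Supine for 5 mins at Screening and at 3 hours after second dose on Day 7". The synopsis, Protocol 5.1 and SAP 3 also set the ECG "at 3 hours after the second dose on Day 7". Protocol 9.1.3 is less specific: "at Screening and 3 hours after dosing on Day 7 during the MAD portion". The ECG row of Table 2 is marked at Screening and Day 7 only.

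**PK labels.** Table 3 flags the Day 7 sample at 12 h (BID) or 8 h (TID) as pre-dose. Protocol 5.1 states "Blood samples will also be collected on Days 2, 4, 6, and 8 before dosing", although Table 2 schedules no dose on Day 8.

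**The concern.** Two footnotes to one table cannot both be carried out. A site that follows footnote a has no second Day 7 dose from which to time the ECG. A site that gives a second dose so as to meet footnote c breaks footnote a. Protocol 9 requires adherence to the Schedule of Activities and allows no waivers, so the site has no sanctioned way out.

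Two things depend on this. The first is the number of doses taken, in a study whose primary objectives include the safety of the multiple-dose regimen. The second is the dose that precedes the only on-treatment MAD ECG. SAP 2.2.1 lists ECG change from baseline among the primary outcome measures. SAP 5.3 uses visits as reported and SAP 8.4 summarizes ECGs by visit, so a Day 7 row would not show which dose came before the recording. That dose also differs in its conditions: the morning dose follows an overnight fast and comes with a standardized light meal, while later doses come with a snack.

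**Working it through.** The documents give no figure for this point, so there is none to reproduce. The check is a comparison of passages plus simple counts.

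**Inputs.** Dosing intervals are q12h for BID and q8h for TID (Protocol 5.1). Day 7 dosing is one morning dose (Table 2, footnote a) or the full daily schedule (narrative sections read without an exception). The ECG is 3 h after the second Day 7 dose (footnote c, Protocol 1 and 5.1, SAP 3) or 3 h after an unnumbered Day 7 dose (Protocol 9.1.3). I assume the stated intervals are kept and the Day 8 sample is drawn at the clock time of the morning dose.

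**Passages side by side**

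| Place | Second Day 7 dose? |
|---|---|
| Table 2 footnote a (Protocol and SAP) | No |
| Table 2 footnote c; Protocol 1 and 5.1; SAP 3 (ECG sentence) | Required |
| Table 3, Day 7 12 h / 8 h sample flagged pre-dose | Implied |
| Protocol 1 and 5.1; SAP 3 (dosing sentences) | Implied by the absence of an exception |
| Objectives and cohort lists (7 days) | Suggested, but could be shorthand |
| Protocol 9.1.3 | Silent; workable either way |

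**Counts**, with k doses per day (2 or 3) and interval τ (12 h or 8 h)

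| Quantity | Formula | BID | TID |
|---|---|---|---|
| Total doses, footnote a | 6k + 1 | 13 | 19 |
| Total doses, seven full days | 7k | 14 | 21 |
| Shortfall under footnote a | (k − 1)/7k | 1/14 = 7.1% | 2/21 = 9.5% |
| Day 7 share of the daily dose, footnote a | 1/k | 1/2 | 1/3 |
| Doses before the ECG, morning-dose anchor | 6k + 1 | 13 | 19 |
| Doses before the ECG, second-dose anchor | 6k + 2 | 14 | 20 |
| ECG after the morning dose, morning-dose anchor | 3 | 3 h | 3 h |
| ECG after the morning dose, second-dose anchor | τ + 3 | 15 h | 11 h |
| Day 8 sample after the last dose, footnote a | 24 | 24 h | 24 h |
| Day 8 sample after the last dose, full Day 7 dosing | 24 − (k − 1)τ | 12 h | 8 h |

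The Day 7 PK profile ends at 12 h (BID) or 8 h (TID). With the second-dose anchor the ECG therefore comes 3 h after the last Day 7 PK sample; with the morning-dose anchor it lies between the 2 h and 4 h samples.

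**Two labelling points stand apart from the contradiction.** The Day 8 before-dosing label is wrong on any reading, because no Day 8 dose is scheduled. The Day 1 sample at 12 h or 8 h carries no pre-dose flag, although a second dose follows it on every reading.

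**The case against.** The conflict between footnotes a and c is not in dispute. The case on the other side is that it matters little and that some of the support is thin.

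- **Small effect.** Under every stated rule the ECG is 3 h after the most recent dose. The readings differ by one or two doses at the end of treatment, and both respect the 2000 mg daily cap. The analysis is descriptive, and the sample size has no statistical basis. The Day 7/Day 1 AUC and Cmax ratios over one interval are unaffected, since the last Day 7 sample precedes any second dose. All of this stands, and it limits the finding to execution and interpretation. It does not make the instruction executable.
- **Weak support.** A morning dose on Days 1 to 7 is compatible with footnote a, the sentence on later doses names no days, and the cohort lines may be shorthand. This is fair: those passages support the point but do not carry it. The conflict rests on footnote a against the second-dose ECG wording, which Protocol 9.1.3 leaves open.
- **Text pointing the other way.** The PK paragraphs list samples before the second daily dose on Days 2, 4 and 6 only, not Day 7. This is weak evidence, because Day 1, which certainly has a second dose, is worded in the same way.
- **The base of 36.** It includes placebo. Participants on ANA001 number at most 3 × 9 = 27, or 3 × 10 = 30 under the 10:2 ratio in the synopsis. For drug exposure those are the right numbers. For following the schedule 36 is correct, because placebo participants also take study doses and have the ECG.
- **The SAP repeats.** The SAP cites the protocol dated 22 October 2020, before Amendment 1, so its copy is not independent evidence. Both footnotes are nevertheless in the current protocol.
- **Flexibility in Protocol 9.5.** It lets the timing of assessments change without an amendment. It does not cover the number of doses.

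**Conclusion.** The concern holds. Table 2 contradicts itself on Day 7, and the second-dose ECG wording recurs in the protocol and SAP narrative. Footnote a gives 13 rather than 14 doses on BID and 19 rather than 21 on TID. The ECG anchor moves from 3 h after the morning dose to 15 h (BID) or 11 h (TID). Up to 36 participants are affected. The counts rest only on the stated dosing intervals; the Day 8 sample times also assume sampling at the morning-dose clock time.

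This must be fixed before MAD dosing, because the schedule cannot be followed as written and the ECG concerned is the single on-treatment MAD recording for a primary safety outcome. No hypothesis test or sample-size figure depends on it. The PK labels are minor and add nothing to the severity.

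**What to change.** 1. Reconcile the Day 7 dosing passages: Protocol Table 2 footnote a, Sections 1 and 5.1, the objectives and the cohort lists, with SAP 2.1, 3 and 3.2. Which schedule applies is for the sponsor to decide.
2. Tie the MAD ECG to one named dose that exists in the reconciled schedule, worded identically in Table 2 footnote c, Protocol 1, 5.1 and 9.1.3, and SAP 3 and 3.2.
3. Record the time from the most recent dose to the ECG, so that the Day 7 summary can be interpreted.
4. Make the Table 3 pre-dose flags agree with the reconciled schedule. The Day 7 flag at 12 h or 8 h changes only if no second Day 7 dose is kept. The Day 1 sample at 12 h or 8 h precedes a second dose in either case and should be flagged.
5. Label the Day 8 sample by time since the last dose.

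The cost is a protocol clarification and matching SAP wording. No visit, ECG or blood sample is added.
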